5.2 Secondary outcomes

Outcome S1:

The number of monthly consultations will be summarized for each participating GP from October 2022 to June 2024. In a stepped wedge analysis model, we will compare the number of consultations sent from primary care BEFORE the intervention to the number of referrals sent AFTER the intervention.

Outcome S2:

We will summarize each participating GPs' answer to stress-related items in the BEFORE and AFTER questionnaire, to calculate the Cohen's PSS sum score (PSS-score).

We will report the mean(SD) or median [IQR] PSS-sum score BEFORE and AFTER for all participating GPs. In addition we will report the frequency of GPs with a PSS sum score ≥ 18 BEFORE and AFTER indicating a high level of stress (2).

Outcome S3:

We will summarize each participating GPs' answer to Job satisfaction-related items in the BEFORE and AFTER questionnaire, to calculate the Warr-Cook-Wall Job satisfaction sum score (WCW-score).

We will report the mean (SD) or median [IQR] WCW-sum score extracted from the 9 sub-items as well as the score of the one overall item BEFORE and AFTER for all participating GPs. In addition, we will report the frequency of GPs with a WCW-sum score ≤ 3 BEFORE and AFTER indicating low job satisfaction (2).

Outcome S4:

We will summarize each participating GPs' answer to burnout-related items in the BEFORE and AFTER questionnaire, to calculate the sum score of the three dimensions in the Maslach Burnout inventory (emotional exhaustion (9 items), de-personalization (5 items), and personal accomplishment (8 items)) (2).

We will report the mean(SD) or median [IQR] sum score for each dimension BEFORE and AFTER for all participating GPs.

Outcome S7:

We will summarize the total number of adverse events reported by the participating GP during the study in relation to the type of ultrasound examination performed.

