Hypothesis P1: For general practice clinics that receive a POCUS intervention the use of POCUS will increase after the intervention evaluated by comparing the number of registered reimbursement codes before the intervention to the number of reimbursement codes registered after the intervention.

(P2) To estimate the effects of a POCUS intervention for primary care clinics on the number of referrals send to secondary care specialists.

Hypothesis P2: For general practice clinics that receive a POCUS intervention the referral rate (number of referrals to hospital or specialist clinics/number of consultations) will decrease evaluated by comparing the referral rate from before the intervention to the referral rate after the intervention.

Secondary objectives:

We will estimate if POCUS leads to change in:

- S1. Number of consultations (e-mail, telephone, video, GP office, visits)
- S2. GPs' perceived stress (Cohen's 10-item Perceived Stress Scale)
- S3. GPs' job satisfaction (Warr-Cook-Wall Job satisfaction Scale)
- S4. GPs' burnout symptoms (Maslach Burnout inventory)
- S5. Healthcare costs

And in addition, we will evaluate:

- S6. Patients experiences following POCUS use
- S7. Adverse events reported by the participating GPs following the intervention
- S8. The patient pathway and the quality of selected POCUS applications used in general practice

Tertiary objectives:

- T1. GPs' experiences of job contentment before and after the intervention
- T2. GPs' experiences of POCUS use in their practice after the intervention
- T3. GPs' experiences of POCUS' influence on perceived stress, job satisfaction and burnout symptoms after the intervention.

8 Trial design

This is a stepped-wedge cluster randomized trial

[figure not shown]
Study process

This research project has been developed following the Medical Research Council's model for developing and evaluating complex interventions²¹ (Figure 1).

Reporting of this trial will follow international guidelines for reporting²² and protocols will follow the SPIRIT statement²³. Before the inclusion of the first participant, the trial protocols will be registered on clinicaltrials.gov.

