This document contains the statistical analysis plan for 'The POCUS IN PRACTICE study Implementation of point-of-care ultrasonography in general practice: A stepped wedge cluster randomized trial'. The aim is to clarify analyses for the intended analyses. Therefore, the statistical analysis plan has been completed prior to the completion of the data collection. The overall purpose is to estimate the effect of a POCUS intervention for general practitioners. In the primary research article, the following outcomes are reported.

The primary outcomes are:

- (P1) The number of registered reimbursement codes sent by the participating GP.
- (P2) The number of referrals send to secondary care by the participating GP.

The secondary outcomes are:

- S1. The number of consultations in primary care (e-mail, telephone, video, visits) managed by the participating GP.
- S2. The GPs' perceived stress (Cohen's 10-item Perceived Stress Scale)
- S3. The GPs' job satisfaction (Warr-Cook-Wall Job satisfaction Scale)
- S4. The GPs burnout symptoms (Maslach Burnout inventory)
- S7. To describe the number of adverse events reported by the participating GPs following the intervention

The tertiary outcome is:

- T3. GPs' experiences of POCUS' influence on perceived stress, job satisfaction and burnout symptoms after the intervention.

The analysis intended for outcomes S5, S6, S8, T1 and T2 will not be specified in this statistical analysis plan, as these outcomes will be specified in elaborating study protocols and reported in separate articles.

The study design involves random and sequential crossover of clusters from control to intervention until all clusters are exposed (1). Participants (General Practitioners) have been recruited from 24th June 2022 to 1st September 2022 representing all five Danish regions. The GPs have been randomized to receive an education at different time-points.

2. Background of the trial

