Type of practice	solo-practice, partnership practice, solo-practice in collaboration, partnership practice in collaboration, other	frequency (%)
Location of practice	rural, city, mixed	frequency (%)
Distance to radiology department	kilometer	Mean (SD) and median (IQR)
Region	North Denmark Region, Central Denmark Region, Region of Southern Denmark, Region Zealand, Capital Region of Denmark	frequency (%)
Number of GPs working in the practice	1-20	Mean (SD) and median (IQR)
Number of patients listed with the clinic	1000-20000	Mean (SD) and median (IQR)

Note: The number of missing for each variable will be reported. ¹ Standard Deviation, ² Inter Quartile Range, ³ General Practitioner, ⁴ Point Of Care Ultra Sound

Characteristics of scanned patients

We will summarize the age and gender of patients being examined with ultrasound during the study according to the scanning-specific remuneration code being used.

5. Outcomes

Following the use of POCUS in the general practice consultations the GPs will follow normal procedures for registration of activities in general practice using remuneration codes, fee-specific codes for using POCUS, and referrals in the medical record system. Prior to this study 11 fee-specific codes for 10 different POCUS examinations and one code for 'any other' POCUS examination will be installed in the medical record system.

For the data analysis of individual GPs activities (P1, P2 and S1), we will receive the number of monthly remuneration codes and referrals for each participating GP from October 2022 to June 2024.

For the data analysis of the GP questionnaires (S2, S3 and S4), we will include only GPs who have responded to both the BEFORE and AFTER questions related to the outcomes.

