5.1. The primary outcomes

Outcome P1:

The number of monthly scanning-specific remuneration codes will be summarized for each participating GP from October 2022 to June 2024. In a stepped wedge analysis model, we will compare the number of scanning-specific remuneration codes BEFORE the intervention to the number of scanning-specific remuneration codes AFTER the intervention.

In addition, we will report the overall frequency of participating GPs, who use the scanning-specific remuneration codes in the end of the study (May and June 2024).

Outcome P2:

The number of monthly referrals will be summarized for each participating GP from October 2022 to June 2024. In a stepped wedge analysis model, we will compare the number of referrals sent by participating GPs BEFORE the intervention to the number of referrals sent AFTER the intervention.

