6.1. Register-based data

From PLSP, we will receive monthly aggregated data extracted from the medical-record system in the participating GPs' clinics from October 2022 to June 2024.

Data will be delivered as monthly aggregated data in separate models:

Model 1: including all scanning-specific remuneration codes registered in the participating clinics by participating GPs and for each code the corresponding age and gender of the patient.

Model 2.1: including the total number of consultations performed in the participating GPs' clinics further specified on the type of consultation.

Model 2.2: including the total number of scanning-specific remuneration codes performed in the participating GPs' clinics further specified on the 11 different codes.

Model 2.3: including the total number of referrals sent from the participating GPs' clinics further specified on the type of referral.

Model 3.1: including the total number of consultations performed by the participating GPs further specified on the type of consultation.

Model 3.2: including the total number of scanning-specific remuneration codes performed by the participating GPs further specified on the 11 different codes.

Model 3.3: including the total number of referrals sent by the participating GPs further specified on the type of referral.

Model 4: including all scanning-specific remuneration codes registered in the participating clinics by participating GPs and for each code, the corresponding type of consultation and any referral sent on the same patient on the same date as the on the same date as the scanning-specific remuneration code was used.

From PLSP, we will also receive a time-trend estimation based on all clinics in Denmark. This estimation will show the general development in number of remuneration code and referrals from October 2022 to June 2024. This data will be used to estimate the underlying time effect which is a confounder for the analysis.

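### The SAP's comparison rule for S1 sets consultations before against referrals after: a drafting slip in a secondary outcome, to be corrected before analysis

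*SAP*

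**What the plan says.** The SAP's opening outcome list defines S1 as "The number of consultations in primary care (e-mail, telephone, video, visits) managed by the participating GP". Protocol section 7 has the same outcome among the things POCUS might change.

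SAP section 5.2, Outcome S1, has two sentences. The first agrees with the definition: "The number of monthly consultations will be summarized for each participating GP from October 2022 to June 2024". The second gives the contrast. The stepped wedge model will "compare the number of consultations sent from primary care BEFORE the intervention to the number of referrals sent AFTER the intervention".

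The neighbouring rule for P2, in SAP section 5.1, is to "compare the number of referrals sent by participating GPs BEFORE the intervention to the number of referrals sent AFTER the intervention".

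On data, SAP section 6.1 lists "Model 3.1: including the total number of consultations performed by the participating GPs further specified on the type of consultation". SAP section 9 names consultations as the third stream of individual GP data and assigns one linear mixed model to P1, P2 and S1. The introduction to SAP section 5 is narrower. For P1, P2 and S1 together it says only that "we will receive the number of monthly remuneration codes and referrals for each participating GP from October 2022 to June 2024". The national time trend used for adjustment (SAP sections 6.1 and 9) is likewise described for remuneration codes and referrals, without consultations.

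**The concern.** The second S1 sentence is the SAP's only statement of the S1 contrast. Section 9 names the model and the data but does not say again what is compared with what. Taken literally, the rule changes the variable at the crossover from control to intervention. The difference between two kinds of activity would then be read as an effect of the training.

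What is at stake is the prespecified analysis of one secondary outcome, the trial's measure of consultation volume in general practice. The SAP says that it was completed before data collection ended, in order to make the intended analyses clear. A rule that the analyst has to reinterpret silently once the data are in weakens that purpose, even when the reinterpretation is obvious.

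**Working it through.** The plan gives no figure to reproduce: there is no assumed consultation rate, referral rate, standard deviation or effect size for S1. The check is a comparison of texts followed by a line of algebra.

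**1. The three register-based rules side by side (SAP sections 5.1 and 5.2)**

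| Outcome | Quantity BEFORE | Quantity AFTER |
|---|---|---|
| P1 | scanning-specific codes | scanning-specific codes |
| P2 | referrals | referrals |
| S1 | consultations | referrals |

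P1 and P2 each compare a quantity with itself. S1 does not. The end of the S1 sentence, from the AFTER quantity onward, is identical to the end of the P2 sentence. The S1 sentence also speaks of consultations as sent, a verb that fits referrals.

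**2. What the written contrast estimates**

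Hold calendar time fixed. For a GP-month, let C0 and C1 be mean consultations without and with the intervention, and R1 mean referrals with it.

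- Target of S1: C1 − C0.
- Contrast as written: R1 − C0 = (C1 − C0) + (R1 − C1).

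The written contrast therefore equals the target plus R1 − C1, the gap between referrals and consultations in the intervention period. With no intervention effect, C1 = C0 = C and R1 = R, so the target is 0 and the written contrast has expectation R − C. This is zero only if R = C. The documents give no value for R or C, so no size can be put on it.

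**3. Whether another part of the plan settles the intent**

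- Protocol section 7 and the SAP's opening list define S1 as consultations.
- The first sentence of the S1 paragraph summarises monthly consultations per GP.
- Protocol section 18a collects the number of consultations for S1.
- SAP section 6.1, Model 3.1, delivers consultations at the level of the individual GP.
- SAP section 9 lists consultations as a data stream for P1, P2 and S1.

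All five point to consultations on both sides. None of them restates the contrast.

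**4. Related gaps that the same edit should close**

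- The data list in the introduction to SAP section 5 covers S1 but does not name consultations.
- The background trend enters the S1 model under SAP section 9 but is described only for remuneration codes and referrals. Remuneration codes might be meant to include consultation codes, but the SAP does not say so. Section 9 itself glosses the term as scanning activity and lists consultations separately.

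**The case against.** The best reply is that this is a copying error and that nobody would act on it. The wording points to P2 as its source, and the sentence just before it names the right variable. The model in SAP section 9 has a single dependent variable, with random effects for clusters and participants and fixed effects for steps. To follow the slip, an analyst would have to build an outcome that is consultations in control months and referrals in intervention months, and nothing in SAP sections 6.1 or 9 describes such a variable. This reply stands, and it keeps the severity low. It does not make the sentence correct, and no other sentence replaces it.

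A reader might infer two stronger points, and the documents support neither.

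- *That the trial would report a large spurious fall in consultations.* Any percentage would rest on an assumed ratio of referrals to consultations. The documents give no such ratio, and the single-outcome model makes the literal analysis unlikely to be run.
- *That the slip spreads to P2, because Hypothesis P2 in Protocol section 7 is a rate with consultations in the denominator.* The slip is in the wording of a contrast and leaves the delivered consultation counts untouched. The SAP's own rule for P2 compares numbers of referrals and uses no denominator.

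**Conclusion.** The point holds as a wording error in an operative analysis rule for a secondary outcome. As written, the S1 contrast compares two different quantities and does not estimate the change in consultations. Its expectation under no effect is R − C, of unknown size. This result needs no assumption beyond mean referrals and mean consultations being different.

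Severity is low. The intended analysis can be recovered from the S1 definition, the first sentence of the S1 paragraph, Model 3.1 and SAP section 9. Design, sample size and data collection are unaffected. For the S1 analysis itself, the unstated background trend is the part of the repair that cannot be read off from elsewhere in the SAP.

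**What to change.** Issue a dated correction to the SAP before analysis, with three changes.

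1. **Section 5.2, Outcome S1.** Replace the second sentence with, for example: *In a stepped wedge analysis model, monthly consultations performed by participating GPs (Model 3.1) BEFORE the intervention will be compared with monthly consultations performed by participating GPs AFTER the intervention.*
2. **Section 5, introduction.** Add consultations to the monthly data listed for P1, P2 and S1, in line with section 9.
3. **Sections 6.1 and 9.** State which national time trend adjusts S1. If remuneration codes in that description are meant to include consultation codes, say so. If they are not, state whether a consultation trend will be obtained or S1 will be analysed without a background trend.

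The first two changes are wording only and use data already scheduled for delivery. The third is also wording only, unless the sponsor finds that the national extract does not cover consultations and decides to request them.

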For the GP questionnaire, we will use validated scales to determine GPs' perceived stress (Cohen's 10-item Perceived Stress Scale), GPs' job satisfaction (Warr-Cook-Wall Job satisfaction Scale) and GPs burnout symptoms (Maslach Burnout inventory). Prior to the study, these questionnaires were tested for face validity in four focus groups with 18 POCUS using GPs (unpublished materiel). The Cohen's 10-item Perceived Stress Scale includes ten items about the frequency of stress-related feelings and thoughts. Each item is rated from 0 (never) to 4 (very often). Previous research has reported a sum score of ≥ 18 to be a high level of stress⁴³. The Warr-Cook-Wall Job satisfaction Scale includes 9 sub-items measuring facets of job satisfaction and one overall item rated on a scale from 1 (extreme dissatisfaction) to 7 (extreme satisfaction). In previous research²⁵ a cut-off on the overall item of ≤ 3 has been used to identify low job satisfaction. The Maslach Burnout inventory consists of 22 items exploring the following three burnout dimensions: (1) emotional exhaustion (9 items) characterised by depletion of emotional resources, (2) depersonalisation (5 items) characterised by emotional detachment from people related to work including patients and (3) personal accomplishment (8 items) including perceived value of work and self-efficacy. All dimensions are rated on a scale from 0 (never) to 6 (every day). A sum score is calculated for each dimension. For each scale, we will calculate a mean sum score with SD and a median sum score with IQR.

For the tertiary outcomes, we will use items previously developed and validated in Danish general practice measuring aspects of GP's job contentment (outcome T1):

- To which degree do you feel you have the job satisfaction du desire? (to a very high degree, to a high degree, to some degree, to a low degree, not at all, I do not know)
- Do you feel that you are respected by to medical colleagues at the hospital? (to a very high degree, to a high degree, to some degree, to a low degree, not at all, I do not know)
- Do you feel appreciated as a general practitioner in the health care system? (to a very high degree, to a high degree, to some degree, to a low degree, not at all, I do not know)
- Do you feel that you are burdened by a need to keep yourself professional up-to-date (to a very high degree, to a high degree, to some degree, to a low degree, not at all, I do not know)

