And finally, the GPs will be asked to declare on a 5-point-likerts scale if they agree or disagree that POCUS use had influenced their sense of perceived stress, job satisfaction or burnout symptoms (outcome T3).

The GP questionnaire will be distributed to participating GPs prior to the educational intervention and after the educational intervention (see Figure 2).

Patient questionnaire (secondary outcome S6)

A patient questionnaire will be delivered to all patients (≥ 18 years old) examined with POCUS, who will be able to provide an informed consent, in month 5-6 after the educational intervention (See Figure 2). The participating GPs will deliver the questionnaire to the patient after the consultation. Patients will fill out the questionnaires themselves on their own mobile devices using a QR code (or alternatively a paper questionnaire). We will use items previously developed and validated⁴⁴. The patients will be asked to declare on a 5-point-likert scale:

- If they felt informed about the purpose of the POCUS examination
- If they felt informed about the results of the POCUS examination
- If they were informed about the difference between POCUS and traditional ultrasound examinations
- If they thought the POCUS examination was a natural part of the consultation?
- If they thought the POCUS examination was disturbing in the consultation with the doctor?
- If they thought the contact between the doctor and themselves was improved or worsened?
- If they thought the ultrasound examination gave them a better or poorer understanding of their health problem?
- If they felt more thoroughly or less thoroughly examined after the ultrasound examination?
- If they felt more or less taken seriously.
- If they felt more or less secure?
- If they thought the ultrasound examination had a large or small impact on the treatment they received?
- If their confidence in the GPs assessment of their health problem had increased or decreased?
- If they thought the ultrasound examination makes the level of service at the GP's office increase or decrease?
- If they thought the ultrasound examination makes the quality in care at the GP's office increase or decrease?
- Their overall experience with the ultrasound examination performed by the physician?

The were also asked to declare on a scale from 1-10:

- How likely they were to recommend the ultrasound examination to other patients having the same health problem and the same physician? (NPT score)

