5.3 Tertiary outcomes

Outcome T3:

We will summarize the participating GPs' experiences of POCUS' influence on perceived stress, job satisfaction and burnout symptoms after the intervention and report the frequency of GPs who report POCUS to have a positive impact (Very decreased or decreased sense of stress/jobsatisfaction/sense of burnout), no impact, or a negative impact (Very increased or increased sense of stress/jobsatisfaction/sense of burnout).

6. Data collection

Data will be collected as specified in the study protocol.

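### Two descriptive rules in the SAP are wrong as written: the S3 cut-off for low job satisfaction cannot be reached, and T3 counts decreased job satisfaction as a positive impact

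*SAP*

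**What the plan says.** **S3, job satisfaction.** Protocol section 12 (GP questionnaire) says that the Warr-Cook-Wall (WCW) scale "includes 9 sub-items measuring facets of job satisfaction and one overall item rated on a scale from 1 (extreme dissatisfaction) to 7 (extreme satisfaction"). On low satisfaction it says that in previous research "a cut-off on the overall item of ≤ 3 has been used to identify low job satisfaction".

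SAP 5.2 plans to report the mean or median "WCW-sum score extracted from the 9 sub-items as well as the score of the one overall item BEFORE and AFTER". The sum score is therefore made of the nine sub-items, and the overall item is a separate quantity. The sentence that follows sets the low-satisfaction rule: "we will report the frequency of GPs with a WCW-sum score ≤ 3 BEFORE and AFTER indicating low job satisfaction".

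**T3, perceived influence of POCUS.** SAP 5.3 sorts GPs into three groups. The first is "positive impact (Very decreased or decreased sense of stress/jobsatisfaction/sense of burnout"), the second is no impact, and the third is "negative impact (Very increased or increased sense of stress/jobsatisfaction/sense of burnout"). Protocol section 12 describes the same outcome as a 5-point Likert item on which GPs state "if they agree or disagree that POCUS use had influenced their sense of perceived stress, job satisfaction or burnout symptoms (outcome T3").

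**S1, for completeness.** SAP 5.2 says "we will compare the number of consultations sent from primary care BEFORE the intervention to the number of referrals sent AFTER the intervention".

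**The concern.** The S3 rule moves a cut-off meant for a single item onto a sum of nine. The same number then falls below the lowest possible score, and the planned frequency stops depending on the data.

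The T3 rule treats three feelings as if a decrease were good for each. For stress and burnout it is; for job satisfaction it is not. The T3 categories also presuppose answers running from decreased to increased, whereas the protocol describes agreement that an influence took place.

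The SAP's opening outcome list places S3 and T3 in the primary research article, and protocol section 6 says it will be important to evaluate how POCUS affects the GP population. An S3 result of 0% would tell readers that no GP had low job satisfaction at either time. A reversed T3 result would report GPs who gained satisfaction as harmed. The second error is the harder to catch, because swapped percentages look entirely plausible.

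**Working it through.** **S3: can the rule be met?**

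Inputs: nine sub-items and one overall item, lowest score 1, highest 7 (protocol section 12); sum taken over the nine sub-items (SAP 5.2); cut-off 3 or less (both documents). Lowest sum = items × 1; highest sum = items × 7.

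| Quantity the cut-off is applied to | Lowest | Highest | 3 or less possible? |
|---|---|---|---|
| Sum of nine sub-items (SAP rule) | 9 × 1 = 9 | 9 × 7 = 63 | No |
| Sum with the overall item added | 10 × 1 = 10 | 10 × 7 = 70 | No |
| Overall item alone (protocol rule) | 1 | 7 | Yes: scores 1, 2 and 3 |
| Mean of nine sub-items | 1 | 7 | Yes: sum of 3 × 9 = 27 or less |

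The SAP rule gives 0% before, 0% after and a difference of 0 for any set of answers.

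The protocol sentence could be read as attaching the 1-to-7 range to the overall item only. The result hardly depends on that. A nine-item sum can reach 3 only if the lowest item score is at most 3/9 = 0.33. Coding the items 0 to 6 would allow it (sum 0 to 54), but neither document describes such coding for this scale. The upper end of the scale plays no part.

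The S2 rule in the same section has no such problem: ten items scored 0 to 4 give a sum from 0 to 40, and its cut-off of 18 lies inside that range.

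*Illustration only.* The documents give no prevalence of low job satisfaction. Assume 5% to 15% of GPs score 3 or less on the overall item, and take all 200 as responders: 0.05 × 200 = 10 and 0.15 × 200 = 30. So 10 to 30 GPs would be reported as none. The base of 200 is a ceiling, because SAP sections 5 and 9 keep only GPs who answered both questionnaires.

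**T3: is the direction right?**

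The documents themselves treat more job satisfaction as better. Protocol section 6 reports early adopters naming an increase as a benefit, section 12 puts extreme satisfaction at the top of the scale, and SAP 5.2 flags low satisfaction.

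| Domain | Favourable direction | Counted as positive in SAP 5.3 | Result |
|---|---|---|---|
| Stress | Decrease | Decrease | Correct |
| Job satisfaction | Increase | Decrease | Reversed |
| Burnout | Decrease | Decrease | Correct |

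If the five options run from very decreased to very increased, one is neutral and correctly placed, and 5 − 1 = 4 receive the wrong sign for job satisfaction.

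**T3: do the response formats agree?**

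If the item is as the protocol words it, a GP who agrees that POCUS influenced their stress has not said which way. Positive and negative impact could then be derived for none of the three domains. If the questionnaire offered the directional options that the SAP implies, only the job-satisfaction sign is wrong. The questionnaire itself is not reproduced, so the documents do not settle which case applies.

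**The case against.** The strongest reply is that these are drafting slips that a competent analyst would repair. The protocol already contains the right S3 rule, the SAP reports the overall item in the sentence before, and a frequency of 0% at both times would be noticed. For T3, the bracketed list can be read as shorthand, and the background section shows which direction was meant.

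Part of this stands. The intended S3 rule is not in doubt, and the remaining S3 summaries are sound. But an S3 error noticed only from its result is repaired after the data are seen, and more than one repair is then available: the overall item, or a nine-item mean of 3 or less. The two can give different frequencies. The T3 reversal gives no warning of its own, and a background remark is not a coding rule.

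The response-format point is rightly called the least certain. The protocol may only be paraphrasing the questionnaire, and the SAP is the later text, so its directional options may be the real ones. That is why the point asks only for the options to be stated and the two documents reconciled. The prevalence illustration rests on an assumption, and the conclusion does not need it. The S1 sentence is a copying slip: the SAP's outcome list, section 6.1 and section 9 make the intended comparison clear, and it adds nothing to the seriousness of this point.

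**Conclusion.** Both rules are wrong as written and should be corrected.

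- **S3:** the planned frequency of low job satisfaction is fixed at 0% before and after. The only condition is that the lowest sub-item score exceeds 0.33, which the protocol's scale meets.
- **T3:** the job-satisfaction result is reversed if the response options are directional. If they are agree/disagree without direction, the planned classification is not available for any of the three domains.

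The reach is limited to one supplementary frequency of a secondary outcome and one tertiary descriptive outcome. P1, P2, S2, S4, the S3 mean or median sum score and the S3 overall-item score are unaffected. Confidence is high on the S3 cut-off and the T3 direction. The consequence of the format mismatch depends on the questionnaire.

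**What to change.** 1. **SAP 5.2, S3.** Apply the cut-off of 3 or less to the overall WCW item, as in protocol section 12. Leave the planned sum-score and overall-item summaries unchanged.
2. **SAP 5.3, T3.** For job satisfaction only, define increased or very increased as positive and decreased or very decreased as negative. Keep the present direction for stress and burnout.
3. **T3 response options.** State the wording used in the questionnaire sent after the intervention, and reconcile SAP 5.3 with protocol section 12. If the item recorded no direction, say so and report agreement only.
4. **SAP 5.2, S1.** In the same edit, correct the sentence so that consultations before are compared with consultations after.

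The cost is two rule sentences, one copying correction and a look at the questionnaire. The overall item is already collected and reported, so no new data are needed. The edits should be made and dated before the questionnaire data are analysed.
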